STUDY PROTOCOL DOCUMENT

Document Title:

Detailed Description of Study Procedures and Statistical Analysis

Document Update Date:

14 January 2026

Prepared for:

ClinicalTrials.gov Registration

Detailed Description

This study was conducted with individuals who agreed to participate voluntarily. Face-to-face interviews were carried out under pandemic precautions, participants were informed about the study, and written informed consent was obtained.

Control Group

Participants in the control group completed baseline assessments including the Sociodemographic Characteristics Form, BBÜRDÖ, and the Pressure Injury Knowledge Test for Wheelchair Users via online forms administered simultaneously with telephone interviews. For participants with existing pressure injuries, home visits were conducted under pandemic precautions, and the Pressure Ulcer Scale for Healing (PUSH) was applied during baseline, follow-up, and post-test assessments.

After completion of the intervention group's training sessions, the control group was followed weekly for 12 weeks. During follow-up, the BBÜRDÖ and Pressure Injury Follow-up Form were administered via telephone interviews. No preventive pressure injury interventions were applied to the control group to avoid influencing knowledge outcomes. Routine counseling was not provided; participants were referred to healthcare services only upon request.

At the end of the 12-week follow-up period, post-test assessments were conducted using the BBÜRDÖ, Pressure Injury Knowledge Test for Wheelchair Users, and Pressure Injury Follow-up Form. Home visits were performed for participants with existing or newly developed pressure injuries, and the PUSH scale was applied. After completion of post-tests, educational sessions were offered to the control group.

Intervention Group

Baseline assessments in the intervention group included the Sociodemographic Characteristics Form, BBÜRDÖ, Pressure Injury Knowledge Test for Wheelchair Users, and Pressure Injury Follow-up Form, administered online with concurrent telephone interviews. Home visits were conducted for participants with existing pressure injuries, and the PUSH scale was applied.

Participants attended structured educational sessions delivered online via Zoom. Four training groups (9–10 participants per group) completed three interactive sessions over two weeks. Each session lasted 60 minutes and covered pressure injury definition, etiology, risk factors, prevention strategies, and care practices. Educational materials were shared prior to the sessions, and a WhatsApp group was created to facilitate communication and interaction.

Following the training sessions, participants received weekly follow-up for 12 weeks with individualized counseling based on their needs. During follow-up, the BBÜRDÖ and Pressure Injury Follow-up Form were administered via telephone interviews. Participants who implemented at least one pressure injury prevention intervention were considered compliant. Home visits were conducted for participants with existing or newly developed pressure injuries, and the PUSH scale was applied.

Statistical Analysis

The study included 78 participants. Data were analyzed using IBM SPSS Statistics version 23. Descriptive statistics were used for categorical and numerical variables. Independent samples t-test and Mann–Whitney U test were used for between-group comparisons. Changes over time were analyzed using paired samples t-test, repeated measures analysis of variance, Cochran's Q test, and Wilcoxon test. Chi-square test was used for categorical comparisons. Statistical significance was set at $p < 0.05$.

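### Follow-up injuries are found by telephone and only known ones are seen, while one arm alone is educated: incidence and pooled PUSH comparisons are open to differential detection

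*Combined protocol and SAP*

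**What the plan says.** The combined protocol and SAP describes the same weekly channel in the Control Group and Intervention Group sections: "During follow-up, the BBÜRDÖ and Pressure Injury Follow-up Form were administered via telephone interviews". In-person assessment depends on an injury being known. The Intervention Group text says "Home visits were conducted for participants with existing or newly developed pressure injuries, and the PUSH scale was applied"; the Control Group text, in its post-test paragraph, says "Home visits were performed for participants with existing or newly developed pressure injuries, and the PUSH scale was applied". Neither section describes a skin check of participants without a known injury, or a rater blinded to arm.

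The arms differ in what they learn before post-test. The intervention sessions "covered pressure injury definition, etiology, risk factors, prevention strategies, and care practices", and are followed by 12 weeks of individual counselling. Controls receive no routine counselling and are offered education only after their post-tests.

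Two further differences appear in the text. For controls, visits for newly developed injuries are mentioned only at post-test, and PUSH during follow-up is stated only for existing injuries; in the intervention arm, visits for new injuries sit within the follow-up paragraph. The Pressure Injury Follow-up Form is listed at baseline for the intervention arm only.

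The Statistical Analysis section lists t, Mann–Whitney and other tests without assigning them to variables. For categorical data it says "Chi-square test was used for categorical comparisons". It contains no provision for unequal detection.

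**The concern.** As described, a new injury enters the data when a participant reports it by telephone, and a PUSH score follows from that report. A visit can overturn a false report but cannot find an injury nobody mentioned. If education and counselling change how readily a participant notices or mentions skin damage, the recorded count reflects detection as well as occurrence.

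If the trained arm detects more, the two injury measures are biased in opposite directions. Its recorded incidence rises, which can mask prevention or resemble harm. The extra injuries are likely to be mild, so its mean PUSH score falls, which can resemble better healing. If trained participants instead under-report to the team that counselled them, the incidence bias reverses and benefit is exaggerated. The second PUSH problem is structural: adding injuries that first appear after training selects on an event that training may itself affect.

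**Working it through.** The plan states no injury rate, PUSH standard deviation, detection rate or power calculation, so there is no figure of its own to reproduce. What follows is an illustration.

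**Inputs from the documents**
- Total: "The study included 78 participants".
- Intervention arm: "Four training groups (9–10 participants per group) completed three interactive sessions over two weeks", so 4 × 9 = 36 to 4 × 10 = 40, leaving 38 to 42 controls. I use 39 per arm.
- Significance level 0.05, taken as two-sided.

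**Assumptions**
- 8 per arm have an injury at baseline, leaving 39 − 8 = 31 at risk of a new one.
- True new-injury risk is 25% in both arms, and half of new injuries are mild.
- Mild injuries are detected 90% of the time in the trained arm and 60%, 40% or 20% of the time in controls; other injuries 95% in both.
- No false reports are counted.
- Mild new injuries score 1.5 SD below the rest.

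**Incidence.** Observed risk = true risk × sensitivity.
- Intervention sensitivity: 0.5 × 0.90 + 0.5 × 0.95 = 0.925.
- Control sensitivity: 0.5 × {0.60, 0.40, 0.20} + 0.5 × 0.95 = 0.775, 0.675, 0.575.

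| Control sensitivity | Apparent RR, no true effect | Apparent RR, true RR 0.70 | Chi-square rejection, no true effect |
|---|---|---|---|
| 0.775 | 0.925/0.775 = 1.19 | 0.84 | 6.4% |
| 0.675 | 0.925/0.675 = 1.37 | 0.96 | 9.3% |
| 0.575 | 0.925/0.575 = 1.61 | 1.13 | 14.0% |

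Rejection rates are from exact binomial enumeration of the uncorrected chi-square test with 31 per arm. Equal sensitivity of 0.925 in both arms gives a ratio of 1.00 and 5.0%.

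**Opposite direction.** With sensitivity 0.70 in the trained arm and 0.90 in controls, true risks of 20% and 40% (RR 0.50) are recorded as 14% and 36%, an apparent RR of 0.39.

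**Pooled PUSH, no true effect (expected counts).** True new injuries per arm are 31 × 0.25 = 7.75, of which 3.875 are mild and 3.875 are not. Non-mild injuries detected in each arm: 3.875 × 0.95 = 3.68.
- Intervention: mild detected 3.875 × 0.90 = 3.49; pool 8 + 3.68 + 3.49 = 15.17; mild share 0.230.
- Control: mild detected 2.325, 1.55 or 0.775; pool 14.01, 13.23 or 12.46; mild share 0.166, 0.117 or 0.062.
- Shift = −1.5 × (0.230 − control share) = −0.10, −0.17 or −0.25 SD, favouring training.

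**Precision of PUSH.** The standard error of the pooled difference is √(1/15.17 + 1/14.01) = 0.37 SD in the first case and √(1/15.17 + 1/12.46) = 0.38 SD in the last. Restricted to 8 baseline injuries per arm it is √(1/8 + 1/8) = 0.50 SD. Late-detected injuries cannot enter the restricted comparison, so this source of shift is removed by construction; that is a property of the restriction and not evidence that the comparison is unbiased.

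**The case against.** The strongest reply is that this is a generic ascertainment limitation, and small beside the imprecision. On the same inputs the pooled PUSH shift is below one standard error, rejection in the mildest case is 6.4% against a nominal 5%, and even with perfect detection the power for a true risk ratio of 0.70 from a 25% risk is only about 11% (31 per arm) to 13% (39 per arm). Every rate is assumed. All of that stands, and it limits how much weight the figures can carry. It does not remove the problem: low power widens the interval, whereas differential detection moves its centre, and the plan addresses neither.

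A reader might infer more than the text supports. The curriculum names definition, etiology, risk factors, prevention and care; it does not say that recognition or skin inspection was taught. Telephone as the first point of detection is also inferred, although it is the only follow-up channel described. Incidence and a between-arm PUSH comparison are implied by the instruments and tests, not named as outcomes. With no detection rates or results given, one cannot say that the comparisons are distorted, or which way. Nor can one say that baseline injuries are free of the bias: they were identified remotely too, the Follow-up Form is listed at baseline for one arm only, and no blinded rater is described.

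An adjustment that allowed only for better detection in the trained arm would also be unfair, since every correction would then favour training.

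**Conclusion.** The concern holds in a limited form. Telephone ascertainment, in-person assessment of known injuries only and education in one arm leave new-injury incidence and pooled PUSH open to differential detection, and nothing in the plan mitigates it. Its size is unknown and its direction uncertain. Under the stated assumptions, better detection after training would produce an apparent risk ratio of 1.19 to 1.61 when there is no effect, and a pooled PUSH shift of about −0.10 to −0.25 SD; under-reporting by the trained arm would push incidence the other way. These are illustrations of what is possible and not estimates for this trial. PUSH in participants whose injury was scored at baseline is less exposed, because those injuries were known before training. The change is worth making because it uses data already collected.

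**What to change.** 1. Make the between-arm PUSH comparison only in participants whose injury was present and scored at baseline. Report PUSH for newly developed injuries descriptively, by arm. State that the restricted comparison is less exposed to this bias but not free of it.

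2. If incidence is compared, report the risk ratio with a two-sided detection-sensitivity table: corrected ratio = observed ratio × (control sensitivity ÷ intervention sensitivity), for sensitivity ratios from about 0.5 to 1.3. The upper end covers under-reporting by the trained arm (0.90/0.70 = 1.29). For example, an observed 1.37 corrects to 0.69 at 0.5 and 1.78 at 1.3; an observed 0.70 corrects to 0.35 and 0.91. Give the sensitivity ratio at which the conclusion changes, and apply the same caution whether that conclusion is benefit, no effect or harm. Note that the formula assumes no false reports are counted.

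3. Reconcile the Control Group and Intervention Group text on when newly reported injuries were visited. Do not require visit confirmation before counting a new injury unless visits were made equally in both arms. Otherwise a control injury that was reported early and healed before post-test could be dropped while its intervention counterpart is counted.

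The document is written in the past tense, so changes to the weekly calls are not available; items 1 and 2 need only analysis wording and one table. The cost is fewer participants in the PUSH comparison (on the assumed counts, a standard error of 0.50 SD instead of about 0.37 to 0.38) and a more cautious incidence conclusion.

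### Between-group score comparisons make no baseline adjustment, although baseline Knowledge Test and BBÜRDÖ scores exist in both arms; ANCOVA would be more precise and less exposed to baseline imbalance

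*Combined protocol and SAP*

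**What the plan says.** The Statistical Analysis section gives one sentence to comparing scores between arms: "Independent samples t-test and Mann–Whitney U test were used for between-group comparisons". Categorical data get a separate, also unadjusted, method: "Chi-square test was used for categorical comparisons". A further sentence covers time: "Changes over time were analyzed using paired samples t-test, repeated measures analysis of variance, Cochran's Q test, and Wilcoxon test". It mentions neither a group factor nor a group-by-time term. No covariate-adjusted model appears anywhere.

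Both scores were measured before the intervention in both arms. Control participants "completed baseline assessments including the Sociodemographic Characteristics Form, BBÜRDÖ, and the Pressure Injury Knowledge Test for Wheelchair Users". For the other arm, "Baseline assessments in the intervention group included the Sociodemographic Characteristics Form, BBÜRDÖ, Pressure Injury Knowledge Test for Wheelchair Users, and Pressure Injury Follow-up Form". At 12 weeks the Control Group section records that "post-test assessments were conducted using the BBÜRDÖ, Pressure Injury Knowledge Test for Wheelchair Users, and Pressure Injury Follow-up Form". The Intervention Group section has no matching post-test paragraph, so I take it that the same instruments were used there.

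The document does not say whether the two-sample tests were applied to post-test scores or to changes from baseline. It also describes no randomisation, stratification or matching.

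**The concern.** In a pre-test/post-test trial of education, a participant's baseline score is usually the best available predictor of the final score. A two-sample test on post-scores leaves that information out. A two-sample test on changes uses it, but with a fixed coefficient of 1 instead of one estimated from the data. In both cases the error variance is larger than it need be.

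Both also react to baseline imbalance. A post-score comparison carries over a share of the baseline difference, and a change-score comparison over-corrects for it. With 78 participants, a baseline difference large enough to matter can arise by chance. Where allocation is not described, it might also be systematic. At stake are the width of the interval and the trustworthiness of the point estimate for the trial's main question: whether the education raised knowledge and changed the BBÜRDÖ score.

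**Working it through.** The document gives no effect size, SD, power or sample-size derivation, so there is no figure to reproduce. What follows is an illustration.

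**Inputs from the document**
- "The study included 78 participants".
- Four training groups of 9–10 give an intervention arm of 36 to 40, leaving 42 to 38 controls if all 78 belong to the two arms. I use 39 and 39. The factor sqrt(1/n1 + 1/n2) is 0.227 at 36/42, 0.227 at 40/38 and 0.226 at 39/39, so the split hardly matters.
- Significance level 0.05. I assume it is two-sided, which is not stated.

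**Assumptions not in the document**
- Scores are roughly continuous with SD 1 at both times.
- The true effect is 0.5 SD.
- The baseline-to-post correlation r is 0.3, 0.5 or 0.7.

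**Variance of each comparison, relative to post-scores**
- Post-scores: 1
- Change scores: 2(1 − r)
- ANCOVA: 1 − r²

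The change-score variance divided by the ANCOVA variance is 2(1 − r)/(1 − r²) = 2/(1 + r), which exceeds 1 for every r below 1. The post-score variance divided by the ANCOVA variance is 1/(1 − r²), which exceeds 1 whenever r is not zero.

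**Power** (noncentral t, 39 per arm, standardised effect = 0.5/sqrt(relative variance))

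| r | ANCOVA variance | Change variance | Post-score power | Change-score power | ANCOVA power | N matching ANCOVA, 78/(1 − r²) |
|---|---|---|---|---|---|---|
| 0.3 | 0.91 | 1.40 | 59% | 45% | 63% | 86 |
| 0.5 | 0.75 | 1.00 | 59% | 59% | 71% | 104 |
| 0.7 | 0.51 | 0.60 | 59% | 80% | 86% | 153 |

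The last column is the number of participants that a post-score comparison would need to match ANCOVA on 78.

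**Repeated measures ANOVA.** Suppose it did include a group factor. With baseline and post-test as the two time points, its group-by-time test is the change-score t-test, so the change-score column applies. An analysis of the weekly BBÜRDÖ values would be a different model, and the text does not specify one.

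**Baseline imbalance.** Under random allocation the baseline difference has standard error sqrt(2/39) = 0.226 SD, with a 95% range of about ±0.44 SD. A difference of b shifts the post-score estimate by r × b and the change-score estimate by (r − 1) × b. For b = 0.3 and r = 0.5 these are +0.15 SD and −0.15 SD. ANCOVA removes the shift under a linear model.

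**Conditional type I error of the post-score test, given b**

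| b (SD) | r = 0.5 | r = 0.7 |
|---|---|---|
| 0 | about 2% | about 0.5% |
| 0.226 | about 4.5% | about 3.5% |
| 0.44 | about 12% | about 19% |

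Averaged over random allocation it is 5%.

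**The case against.** The strongest reply is that the plan may already use baseline. A t-test or Mann–Whitney test on change scores does so, and a repeated measures ANOVA is listed. A reader might infer that baseline data were ignored altogether. The document does not support that, because it leaves open which score was compared and whether the ANOVA had a group factor. On the change-score reading the gap at r = 0.7 is 80% against 86%, far smaller than 59% against 86%. This limits the size of the point but does not remove it, since ANCOVA is more precise on either reading.

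A reader might also infer that the tests have an inflated false-positive rate, or that the arms probably differed at baseline. Neither follows. The 12% to 19% conditional error applies only at the edge of the chance range, and at a typical imbalance the error is below 5%. A text that does not describe randomisation does not show that there was none. It means only that systematic differences cannot be ruled out. If they exist, adjusting for baseline scores deals with those scores and nothing unmeasured.

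Three further limits stand. The gain depends on an unknown r, and at 0.3 it is only about four power points over post-scores. The document does not describe how BBÜRDÖ is scored, so a linear model may not suit it. The analysis is reported in the past tense: power can no longer change the sample, and any new model is chosen after the event.

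**Conclusion.** The point holds as a weakness of efficiency and conditional bias, and is a should-fix. The named between-group tests have no baseline adjustment, while the data for it were collected in both arms. Whether post-scores or changes were compared, and even if the repeated measures ANOVA tested group by time on baseline and post-test, the comparison is less precise than ANCOVA and sensitive to baseline imbalance.

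At r = 0.5 the unadjusted variance is 1/0.75 = 1.33 times that of ANCOVA on either reading. At r = 0.7 it is 1/0.51 = 1.96 times for post-scores and 0.60/0.51 = 1.18 times for change scores. These ratios assume continuous scores, equal SDs and a linear relation. The power figures also assume a 0.5 SD effect. The Mann–Whitney test was not modelled separately; it too takes no covariate.

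The documents do not support calling the stated tests invalid. Under random allocation they hold their nominal error rate on average.

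**What to change.** State whether the two-sample tests compared post-test or change scores, and whether the repeated measures ANOVA had a group factor.

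Then report an ANCOVA of the 12-week Knowledge Test score on arm and baseline Knowledge Test score. Do the same for BBÜRDÖ if its scoring suits a linear model. Give the adjusted mean difference with a 95% confidence interval, using robust or bootstrap intervals if residuals are skewed.

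Label this as a revised or supplementary analysis and show it beside the results of the stated tests. Add two cautions. Adjustment covers only measured baseline covariates. Individual-level intervals take no account of the education having been delivered in four training groups, so they may be too narrow.

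The cost is a paragraph of text and a small re-analysis of data already held. The downside is that the adjusted model is post hoc, which the labelling must make plain.

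### No between-arm test of change is specified: the listed tests of change either contain no arm term or do not state one, and nothing ranks between-arm results above within-arm p-values

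*Combined protocol and SAP*

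**What the plan says.** The Statistical Analysis section of the combined protocol and SAP lists tests by type and does not link them to outcomes. For change it says: "Changes over time were analyzed using paired samples t-test, repeated measures analysis of variance", and the same sentence goes on to add Cochran's Q and Wilcoxon. The sentence just before reads "Independent samples t-test and Mann–Whitney U test were used for between-group comparisons", and the one just after reads "Chi-square test was used for categorical comparisons". No primary outcome, primary contrast, baseline adjustment or decision rule is given. The sample size is stated as "The study included 78 participants", without arm sizes.

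Both arms have longitudinal data. In the Control Group section, "the control group was followed weekly for 12 weeks", with BBÜRDÖ and the injury form taken by telephone, and with BBÜRDÖ and the knowledge test at baseline and post-test. In the Intervention Group section, "participants received weekly follow-up for 12 weeks with individualized counseling based on their needs", using the same two weekly instruments. PUSH is applied in both arms, to participants who have a pressure injury.

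**The concern.** The question for this trial is whether the intervention arm changed more than the control arm. A paired t-test, a Wilcoxon signed-rank test or Cochran's Q asks only whether one set of people changed. Run separately in each arm, these tests give two p-values, and the difference between two p-values is not a test of the difference between arms.

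This matters here because both arms could plausibly change without any intervention effect. Both are telephoned weekly and complete BBÜRDÖ repeatedly. The knowledge test is listed for controls only at baseline and post-test, so the retesting argument is weaker there, but it still applies. Existing injuries may heal in either arm, and extreme baseline values drift back. A control arm removes such shared change only if the analysis compares the arms.

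The between-group tests in the plan could do this, but their target is not stated. They could be a check of baseline comparability, a post-test comparison that ignores baseline, or a comparison of change. The text does not describe how the arms were formed, so baseline similarity cannot be assumed.

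**Working it through.** The plan gives no effect size, SD or power, so there is no design figure to reproduce. The check has two parts.

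**1. Which listed test compares change between arms?**
- Paired t, Wilcoxon and Cochran's Q: no arm term.
- Repeated measures ANOVA: possible with an arm factor and an arm × time term; neither is stated. It would not suit binary injury status in any case.
- Independent t and Mann–Whitney: possible if applied to change scores; not stated.
- Chi-square: compares categories; time point and grouping not stated.

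So some listed methods could make the comparison, but none is specified to do so.

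**2. What would it cost to read significance in the intervention arm only as an effect?**

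Inputs:
- Total of 78 and a 0.05 significance level, from the Statistical Analysis section. Sidedness is not stated; two-sided is assumed.
- Intervention arm: four training groups of 9 or 10 (Intervention Group section) give 4 × 9 = 36 to 4 × 10 = 40, leaving 78 − 36 = 42 to 78 − 40 = 38 controls. A 39/39 split is assumed, and the extremes are also shown.
- The same true change, dz, in both arms, in units of the SD of the change score. The documents give no value, so a range is used.

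Formula: the power p of a paired t-test with n pairs comes from the noncentral t distribution with n − 1 degrees of freedom and noncentrality dz × √n. With independent arms,

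P(intervention significant, control not) = p_I × (1 − p_C).

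For example, with n = 39 and dz = 0.3, the noncentrality is 0.3 × √39 = 1.87 and p = 0.447, so the probability is 0.447 × 0.553 = 0.247.

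| Shared change (dz) | Power in each arm (n = 39) | Intervention significant, control not |
|---|---|---|
| 0 | 0.050 | 4.8% |
| 0.1 | 0.093 | 8.5% |
| 0.2 | 0.230 | 17.7% |
| 0.3 | 0.447 | 24.7% |
| 0.32 | 0.495 | 25.0% (maximum) |
| 0.4 | 0.682 | 21.7% |
| 0.5 | 0.861 | 12.0% |
| 0.6 | 0.955 | 4.3% |
| 0.8 | 0.998 | 0.2% |

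Other splits at dz = 0.32: 36/42 gives 0.463 × (1 − 0.526) = 22.0%; 40/38 gives 0.506 × (1 − 0.485) = 26.1%. At dz = 0.3 the same splits give 21.9% and 25.7%.

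A simulation with 100,000 trials per scenario at 39/39 agrees (24.9% at dz = 0.32). In the same simulated trials, an independent t-test on change scores, which for two time points is the arm × time test, was falsely significant in 4.9% to 5.1% at every dz tried (0, 0.2, 0.32, 0.5, 0.8).

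**The case against.** The strongest reply is that this is a gap in specification, not a planned error. Most of that reply stands.

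- A reader might infer that the plan never compares the arms. It does list between-group tests, on either side of the sentence on change, and the control arm has a week-12 post-test. A two-sample test of post-test or change scores, or a chi-square on injury at week 12, would fit the list. The supportable statement is that no such test of change is specified.
- A reader might infer that every test of change is a single-sample test. Repeated measures ANOVA need not be, and a term that is not stated may still have been fitted.
- A reader might infer that the study will claim efficacy by comparing within-arm p-values. No sentence says so. The error rates above apply only if an author or reader adopts that rule.
- A reader might take about 25% as the error rate. It is the peak, where within-arm power is near 50%. If the shared change is large, both arms become significant and the risk falls below 5%.

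The reply does not close the gap. The targets of the between-group tests remain unknown, no baseline adjustment is stated although baseline values were collected, and for injury status and any outcome sent to Wilcoxon the listed tests of change cannot include the arm.

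**Conclusion.** The concern holds in this limited form: the plan names no between-arm test of change, does not say what its between-group tests are applied to, states no baseline adjustment, and sets no priority between the two kinds of result. If within-arm significance were used as evidence of effect under equal change, the false-positive chance would range from under 1% to about 25%, and would peak at 22–26% over the arm splits compatible with the documents, against about 5% for a direct comparison. This rests on independent arms, two-sided 0.05, t-tests on roughly normal change scores and an assumed common change; it has not been computed for Wilcoxon or Cochran's Q.

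It would go too far to say that the control arm's purpose is lost. Its use is not secured by the text, but a between-group comparison at week 12 would use it. Because this is the study's central inference, the contrast should be fixed before any efficacy statement is made. If the ANOVA already contained an arm × time term, saying so would resolve much of the point for the outcomes it covers.

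**What to change.** State that intervention effects are judged only on between-arm contrasts, each reported as a difference (or ratio) with a confidence interval, and name one per outcome:

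- **Knowledge:** post-test score compared between arms, adjusted for baseline score (ANCOVA). The Intervention Group section does not describe that arm's post-test; this assumes that it matches the control arm's, and the plan should say so.
- **BBÜRDÖ:** one model for both arms with arm, week, arm × week and baseline value, allowing for repeated measures within a participant, reporting the arm difference at week 12. A baseline-adjusted comparison at week 12 alone would be an acceptable equivalent.
- **Injury:** one between-arm comparison of new injury by week 12, stratified by existing injury at baseline, with an exact method if counts are small.
- **PUSH:** baseline-adjusted between-arm comparison among participants with an injury at baseline.

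Keep paired t, Wilcoxon and Cochran's Q results as descriptive only, and state what each independent t, Mann–Whitney and chi-square test is applied to. The documents do not describe the BBÜRDÖ scale or give injury counts, so the exact model form should be confirmed against the data structure.

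Cost: new wording and a re-analysis of data already collected. Some significant within-arm results could no longer be cited as efficacy.
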